Clearing the fog: Is Hydroxychloroquine effective in reducing Corona virus disease 2019 progression: A randomized controlled trial

Registration NO: ID: NCT04491994

Date: 15 May 2020

Study design, setting and participants: This single Centre, parallel open label randomized controlled trial was carried out during 10th April to 31st May 2020 at department of Pulmonology, Pakistan Emirates Military Hospital (PEMH) over 500 patients from both genders between 18-80 years of age. The study design was approved by institutional ethical review committee. The study population was comprised of patients from both genders with Mild confirmed COVID-19 after their written consent. The study protocol and approval documents are available online at ClinicalTrials.gov with trial number of NCT04491994.

Sample size calculation: Sample size was calculated using OPEN EPI with 5% level of Confidence and 80% power to detect a difference and enrolment ration 2:1 between intervention and control group, at a two-sided significance level of $\alpha=0.05$, of 7 days in the median time to clinical improvement between the two groups, assuming that the median time in the SOC group was 14 days and assuming 55% efficacy of HCQ in preventing disease progression and achieving viral clearance at day 7. Calculated sample size was 467, however we used a sample size of 500.

Enrolment procedure: During study period, 672 confirmed PCR positive cases were assessed for eligibility. 132 did not meet selection criteria and subsequently excluded. 540 patients were then enrolled and randomized. Further 20 patients were excluded from analysis as 15 withdrew consent and 5 became symptomatic before first dose of HCQ. During follow up 13 patients were found to be deviated from advised therapy and 7 were lost to follow up yielding a final study population of

500. **Figure 1** summarizes this process. Randomization rules were designed by [name] together with principal investigators and implemented by an independent statistician who was not involved in data analysis. Stratified random sampling was applied to stratify all eligible patients according to age, gender and comorbidities. Computerized random number generator was used and allocation was done in 2:1 sequence. Cards with each group assignment number randomly generated by computer were placed in sequentially numbered envelopes that were opened as the patients were enrolled

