Interventions: A total of 349 patients included in intervention group and 151 in control group. In Hospital, HCQ was given to patients after written consent and after considering its contraindications. Three hundred and forty-nine (349) patients were included in intervention group and given HCQ in addition to standard of care treatment. After 12 hours of randomization HCQ was given. Standard dose of HCQ was 400 mg by mouth twice a day for day one followed by 200 mg 12 hourly for next 5 days. The patients who did not give consent for treatment with HCQ or had a known allergy to HCQ or chloroquine or had another known contraindication to treatment with the study drug, including retinopathy, G6PD deficiency and QT prolongation served as controls. Controls were matched with participants on the basis of age, gender and co morbid and comprised of 151 patients. Standard of care (SOC) treatment comprised of daily oral Vit C (2gms), oral Zinc (50mg), oral Vit-D (alfacalcidol 1ug) and tablet Paracetamol (for body aches/fever), intravenous fluids, hemodynamic monitoring, and laboratory testing for SARS-CoV-2 and baseline blood parameters. Neither patients, nor investigators, nor statisticians were masked to treatment assignment. Lab staff who performed sampling for PCR, basic blood tests and other routine measurement were unaware of treatment information. Data regarding age, co-morbidities, history of contact with a positive patient, days since contact, duration of symptoms, PCR status

with date and base line labs/X-ray chest were recorded. Any patient with day 0 CRP greater than 6mg/dl, Absolute lymphocyte count (ALC) < 1000 or evidence of infiltrates on X-ray chest were excluded. Daily temperature, respiratory rate (RR) and resting O2 saturation with pulse oximetry were monitored in all patients during their hospitalization.

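### The analysed arms (349:151) depart from an exact 2:1 split of the 540 randomised; the readable text gives no counts by arm, so the 40 removals need tabulating and bounding by assigned arm

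*Combined protocol and SAP*

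**What the plan says.** The Sample size calculation section plans an "enrolment ration 2:1 between intervention and control group". The Enrolment procedure section says "540 patients were then enrolled and randomized" and, on the method, "Computerized random number generator was used and allocation was done in 2:1 sequence". It adds that "Stratified random sampling was applied to stratify all eligible patients according to age, gender and comorbidities", and that assignment cards were held in sequentially numbered envelopes. No block size or other restriction is stated.

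The same section gives the removals in two steps: "Further 20 patients were excluded from analysis as 15 withdrew consent and 5 became symptomatic before first dose of HCQ", then "During follow up 13 patients were found to be deviated from advised therapy and 7 were lost to follow up". Neither step is split by arm in the text. Figure 1 is cited as the summary of this flow but is not reproduced in the text available here.

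The Interventions section then states: "A total of 349 patients included in intervention group and 151 in control group". It also says that patients who declined HCQ, or had an allergy or other contraindication to it, made up the controls, and that the 151 controls were matched on age, gender and comorbidity. The Statistical analysis section names t-tests and chi-square tests. It does not define the analysis set or say how removed patients are handled.

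**The concern.** A 2:1 division of 540 is 360 and 180. Set against 349 and 151 analysed, that leaves 11 missing from HCQ and 29 from control. The direction is unexpected: the control arm had no added study drug to stop or deviate from, yet it would have lost the larger share. In an open-label trial, removal can depend on the assigned arm and on early course, so unequal removal could bias both 5-day progression and PCR clearance. The pooled removal figure of 40/540 (7.4%) would not show this.

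If instead removal was equal, the realised allocation was further from 2:1 than a tightly controlled sequence would give. The reader of the text cannot tell which of these happened, or whether either did.

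**Working it through.** **Inputs.** From Enrolment procedure: 672 assessed, 132 not eligible, 540 randomised, removals of 15, 5, 13 and 7. From Interventions: 349 HCQ and 151 control analysed.

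**The plan's own totals reproduce.** 672 - 132 = 540. 540 - 15 - 5 - 13 - 7 = 500 = 349 + 151.

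**Ratio.** 349/151 = 2.31, or 69.8% on HCQ. Exact 2:1 of 500 would be about 333:167.

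**Is 349 of 500 compatible with 2:1?** If each patient had an independent 2/3 chance of HCQ, the exact binomial two-sided p is 0.14 (z = 1.49). Yes.

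**Scenario A, exact 2:1 of 540.**
- 540 × 2/3 = 360; 360 - 349 = 11; 11/360 = 3.1%.
- 540 × 1/3 = 180; 180 - 151 = 29; 29/180 = 16.1%.
- Withdrawals and losses total 15 + 7 = 22. So at least 29 - 22 = 7 of the removed controls must come from the 5 + 13 = 18 who became symptomatic before HCQ or deviated from therapy. If the 5 were all HCQ patients, which is the natural reading but is not stated, the other 35 split 6 HCQ to 29 control.

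**Scenario B, equal removal.**
- 349 × 540/500 = 376.9 and 151 × 540/500 = 163.1, so about 377:163.
- 28/377 = 7.4% and 12/163 = 7.4%.
- 377 of 540 against 2/3: exact p = 0.13.

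**Range.** HCQ assignments from 349 to 381 (of the feasible 349 to 389) are compatible with simple 2:1 at the 5% level. At 349:191, removal is 0/349 = 0% and 40/191 = 20.9%. At 381:159 it is 32/381 = 8.4% and 8/159 = 5.0%. For 371 to 381 on HCQ, removal does not differ significantly between arms.

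**Effect on the primary outcome.** The documents give no progression rate, so I assume 10% in each analysed arm: 35/349 and 15/151. Treat every removed patient as outcome unknown. The lower limit counts all removed controls and no removed HCQ patients as progressing; the upper limit does the reverse.

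| Split | HCQ risk | Control risk | Risk difference (HCQ - control) |
|---|---|---|---|
| 349:191 | 35/349 = 10.0% | 15/191 to 55/191 = 7.9 to 28.8% | -18.8 to +2.2 points |
| 360:180 | 35/360 to 46/360 = 9.7 to 12.8% | 15/180 to 44/180 = 8.3 to 24.4% | -14.7 to +4.4 points |
| 377:163 | 35/377 to 63/377 = 9.3 to 16.7% | 15/163 to 27/163 = 9.2 to 16.6% | -7.3 to +7.5 points |
| 381:159 | 35/381 to 67/381 = 9.2 to 17.6% | 15/159 to 23/159 = 9.4 to 14.5% | -5.3 to +8.2 points |

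At 360:180 with assumed rates of 5% and 20%, the ranges are -15.8 to +3.3 and -13.3 to +5.8 points. These are outer limits: some of the 40, such as those who deviated from therapy, may have recorded outcomes, and using them would narrow the range.

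**The case against.** A reader might infer that 349:151 cannot come from a 2:1 allocation of 540, and hence that controls were removed about five times as often as HCQ patients (16.1% against 3.1%). A significance test of 11/360 against 29/180 would look decisive. The documents do not support that reading, for four reasons.

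- The counts 11 and 29 appear nowhere. They come from subtracting the analysed arms from an assumed exact 360:180. Testing them gives no evidence about what happened.
- No block size is stated. Under simple randomisation, 2:1 can be true and removal equal at the same time, as Scenario B shows. Stratification and pre-numbered cards usually go with restricted randomisation, which makes an exact ratio more plausible, but that is inference.
- Figure 1 may already give the counts by arm. Only the readable text can be said to lack them.
- The Interventions section describes controls as refusers and patients with contraindications, then matched. If that is how the 151 arose, 180 - 151 is not a removal count at all. It also weakens the argument that controls had nothing to refuse.

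All four stand, and they reduce the 3% and 16% to one scenario. They do not remove the need for counts by assigned arm, and they do not touch the bounds: the risk difference can take either sign at each split shown, including the one with equal removal. The compatibility of 349/500 with 2:1 says nothing about whether the 40 removals were balanced.

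**Conclusion.** The point holds in limited form. The analysed ratio departs from an exact 2:1 split of 540. The text available does not show whether the cause is chance in the allocation, unequal removal, or controls being formed by something other than the card list. No arithmetic contradiction is established, and differential removal is not shown.

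What is firm is that 40 of 540 randomised patients (7.4%) are left out, with no stated analysis of all randomised patients. Under an assumed 10% progression in both analysed arms, that is enough to leave the sign of the 5-day risk difference open: 19.1 points wide at 360:180 (-14.7 to +4.4) and 14.8 points wide at 377:163 (-7.3 to +7.5). The size depends on the assumed event rate and on treating all 40 as unknown. The need for the analysis does not depend on the 360:180 assumption.

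**What to change.** 1. From the computer list and numbered envelopes, state in Enrolment procedure how many of the 540 were assigned to each arm, and the block size or other restriction if there was one. If Figure 1 already holds the counts, carry them into the text.
2. Tabulate the 15, 5, 13 and 7 removals by assigned arm. Correct the description of a 2:1 sequence if the list does not show it.
3. Reconcile these counts with the Interventions account of who became a control and of matching, and with the exclusion of patients with contraindications under Inclusion and exclusion criteria. These passages cannot all describe one randomised comparison as they stand.
4. Whatever the split, add to Statistical analysis a sensitivity analysis of 5-day progression in all randomised patients by assigned arm. Use recorded outcomes where they exist and best- and worst-case bounds for the rest, and report it beside the 349 against 151 comparison. The bounds are there to be weighed with the main result; a range crossing zero need not by itself bar a conclusion, since both limits are extreme.

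The cost is a recount of an existing list, one table and one analysis. The downside is a possibly less firm conclusion.

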Operational definitions: A case was considered confirmed on the basis of positivity of RT-PCR of combined Oropharyngeal and Nasopharyngeal swabs. Severity of disease was defined as per criteria designed by WHO¹¹. Mild disease meant Patients with uncomplicated upper respiratory tract viral infection having non-specific symptoms such as low-grade fever (fever < 100F for < 3 days), fatigue, body aches, cough (with or without sputum production), anorexia, muscle pain, sore throat, nasal congestion, anosmia, headache and rarely diarrhea, nausea, and vomiting. PCR sampling was done on day 7 and 14 of admission. Any chronic health condition for which patients were on prior treatment was considered as co morbidity. After start of treatment, development of fever > 101 F for > 72 hours, shortness of breath by minimal exertion (10-Step walk test), derangement of basic lab parameters (ALC < 1000 or raised CRP) or appearance of infiltrates on CXR during course of treatment was labeled as progression irrespective of PCR status. PCR status of patients was checked after 7 days and 14 days of initiation of treatment.

Inclusion and exclusion criteria: Inclusion criteria included (1) Mild Corona virus disease (COVID-19) (2) PCR confirmed infection (3) Hospital admitted patients (4) 18-80 years age Exclusion criteria were (1) Moderate, severe and critical COVID-19 (2) day 0 CRP greater than 6mg/dl, ALC < 1000 or evidence of infiltrates on X-ray chest (3) comorbidity with life expectancy less than 6 months (4) Contraindications to HCQ therapy.

Outcomes: Primary outcome was disease progression within 5 days of start of treatment. This was defined by development of fever > 101 F for > 72 hours, shortness of breath by minimal exertion

(10- Step walk test), derangement of basic lab parameters (ALC < 1000 or raised CRP) or appearance of infiltrates on CXR. Patients underwent 6 hourly axillary temperature check, daily 10 feet walk test, daily Blood counts, CRP and X-Rays on day 0, 3 and 5.

Secondary outcome was Viral clearance. PCR negativity on day 7 and 14 after admission was recorded.

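### The control arm is described both as allocated by randomisation envelope and as made up of patients who refused or could not take HCQ, and the second description also conflicts with exclusion criterion 4

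*Combined protocol and SAP*

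**What the plan says.** **Enrolment procedure.** Of 672 PCR-positive patients assessed, "132 did not meet selection criteria and subsequently excluded", and "540 patients were then enrolled and randomized". On method, "Computerized random number generator was used and allocation was done in 2:1 sequence", and the assignment cards were "placed in sequentially numbered envelopes that were opened as the patients were enrolled". Forty patients were then removed (15 + 5 before treatment, 13 + 7 during follow-up), leaving 500.

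**Interventions.** The groups are 349 on HCQ and 151 controls. The text says "In Hospital, HCQ was given to patients after written consent and after considering its contraindications", and that dosing came 12 hours after randomisation. It then describes the controls: "The patients who did not give consent for treatment with HCQ or had a known allergy to HCQ" or chloroquine, or had another known contraindication, "including retinopathy, G6PD deficiency and QT prolongation served as controls". It adds that controls were matched to participants on age, gender and comorbidity.

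**Inclusion and exclusion criteria.** The last exclusion is "4) Contraindications to HCQ therapy".

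**Statistical analysis.** Only t-tests and chi-square tests are named. No covariate adjustment is described.

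**The concern.** There are two separate conflicts.

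1. **Envelope against refusal or contraindication.** A patient placed in the control arm by declining HCQ, or by being unable to take it, was not placed there by a random card. This applies to everyone covered by the Interventions sentence.
2. **Contraindicated controls against criterion 4.** Patients with a known allergy, retinopathy, G6PD deficiency or QT prolongation should have been screened out and should be in neither arm. This applies only to contraindicated patients; refusing HCQ breaches no listed criterion.

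Three readings are open:

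- **(a)** Envelopes formed both arms, and the Interventions section misdescribes the controls.
- **(b)** Controls were assembled by refusal or contraindication, so the study is not randomised.
- **(c)** Envelopes were opened, and HCQ-allocated patients who then refused or proved contraindicated were counted as controls. The 12-hour gap and the consent check before dosing give this some support.

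Under (b), arm membership depended on patient choice or medical history, either of which may relate to progression. Balancing age, gender and comorbidity would not remove that. Under (c), the same objection applies to the switched patients. As written, a reader cannot tell which comparison the p-value refers to.

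**Working it through.** **Patient flow.** 672 − 132 = 540; 540 − 15 − 5 = 520; 520 − 13 − 7 = 500; 349 + 151 = 500. The stated totals are consistent.

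**Do the arm sizes settle it?** At 2:1, 500 patients would split about 333:167. The observed split is 349:151, or 2.31:1. The exact two-sided binomial test of 349/500 against 2/3 gives p = 0.14. The counts neither confirm nor refute random allocation, so they do not separate (a) from (b).

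**How much can (c) explain?** Let H be the number of HCQ envelopes among the 540 and x the number of final controls who held one. Assume no control-allocated patient was counted as HCQ.

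- HCQ-allocated removals = H − 349 − x
- Control-allocated removals = (540 − H) − (151 − x) = 389 − H + x
- The two sum to 40, as they must.

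Removals cannot be negative, so x ≤ H − 349. The documents do not give H, so a range is shown:

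| H | Basis | Largest x | Share of 151 |
|---|---|---|---|
| 360 | exact 2:1 (assumed) | 11 | 7.3% |
| 370 | intermediate | 21 | 13.9% |
| 381 | upper 97.5% point, simple 2:1 allocation | 32 | 21.2% |
| 500 | needed for all controls to be switched | 151 | 100% |

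The 95% range for H under simple 2:1 allocation is 338 to 381. Half the controls (76) would need H ≥ 425, which has probability about 5 × 10⁻¹⁰. These caps are generous: at the cap, all 40 removals come from the control allocation. If the 5 patients removed before a first HCQ dose were all HCQ-allocated, the first three caps fall to 6, 16 and 27.

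**What selection could do to the test (illustration only).** The documents give no progression rate and no prognosis for refusers, so these rates are assumed. They come from exact enumeration of the two-sided Pearson chi-square at 5%, without continuity correction, for 349 against 151 with no HCQ effect. Reading (b) takes all controls as selected.

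| Base risk | No selection | (b), risk ratio 1.2 | (b), risk ratio 1.5 | (b), risk ratio 0.5 |
|---|---|---|---|---|
| 5% | 5.0% | 8.5% | 21% | 21% |
| 10% | 5.1% | 11% | 37% | 46% |
| 20% | 5.1% | 18% | 68% | 81% |

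For (c), take a risk ratio of 1.5, would-be switchers at share x/(349 + x) in both allocated arms, and the HCQ group left at base risk. At 10% base risk, rejection is about 6%, 7% and 8% for x = 11, 21 and 32. At 20% base risk with x = 32 it is about 12%.

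**The case against.** The strongest reply is that the Interventions wording is loose. On that view the envelopes formed both arms, matching means stratification, and the sentence about refusers describes a few post-randomisation switches. The 12-hour interval and consent check fit this, and the final ratio is compatible with 2:1. Figure 1, which is not available here, may show counts by arm.

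Part of this stands. The matching sentence is supporting evidence only. Under (c) the criterion 4 conflict could be avoided if every switched patient was a refuser, or if the contraindication came to light only after the envelope was opened. The text makes the second escape harder, because it speaks of known contraindications. The three readings are also not exhaustive: a mixed arm, with envelope controls plus non-randomised additions, is possible. The rejection rates depend heavily on assumed inputs, and the direction of any bias is unknown, so they should not decide how serious the point is.

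The rest does not stand. The sentence lists specific conditions and says those patients served as controls. Even as a drafting slip, it misstates the origin of the comparison group. Figure 1 could supply counts, but it would not remove the conflict between the sections.

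**Conclusion.** The contradiction holds with high confidence and must be resolved before any randomised claim is made. Which reading is true cannot be determined from the documents, nor can the number of controls who entered by each route.

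If most controls were refusers or contraindicated, as the Interventions section reads, post-randomisation switching cannot account for it: the limit is 11 of 151 at an exact 2:1 split and 32 at the upper end of simple allocation. That bound rests on the stated flow counts and on no patient having moved from control to HCQ. Under (b), the inflation of false-positive findings could be large. Under (c) it is probably smaller, but the comparison would still not be by allocation.

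**What to change.** 1. From existing envelope, consent and screening records, establish for each of the 540 patients the envelope allocation and route of entry (envelope, refusal, contraindication). Check the result against Figure 1 and show the 40 removals by allocated arm.
2. Reconcile the Enrolment procedure, Interventions and exclusion criteria sections to those facts. Do not simply delete the Interventions sentences, which may be the only disclosure of how controls were assembled.
3. **If envelope allocations exist (a or c):** make the primary comparison by envelope allocation, among patients eligible under criterion 4 on pre-randomisation data. Report any control without an envelope as a separate non-randomised cohort.
4. **If controls were assembled by refusal or contraindication (b):** drop the randomised label from the title and conclusions. Present an observational comparison adjusted for recorded baseline data (age, gender, comorbidities, symptom duration, baseline laboratory values), keeping matched sets if matching was individual. Describe contraindicated patients separately, since adjustment cannot make them comparable with patients able to receive HCQ.

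A related but separate step, needed even if the sentence is a slip, is to return removed patients to their allocated arm where outcome data exist and consent permits, with a sensitivity analysis for the rest. Consent limits this for the 15 who withdrew.

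**Cost.** Record tracing for 540 patients, rewritten sections and possibly a new primary analysis; no new patients or procedures. The randomised control group may shrink or vanish. If only 76 of the 151 had an envelope allocation to control (an assumed figure), the standard error of the risk difference would rise by a factor of √[(1/349 + 1/76)/(1/349 + 1/151)] = 1.30, taking a common event risk in both arms.

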Statistical analysis: Statistical interpretation of data was performed using Statistical Package for Social Sciences (SPSS) version 23. Results were expressed as mean, standard deviation (\pm SD) for all continuous variables and frequency and percentage for categorical data. We used t-test and chi-square test as appropriate to the nature and distribution of the variables. A p-value < 0.05 was considered statistically significant.

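### Statisticians were unmasked while deviation status, the CRP criterion and the progression window had no fixed rule, so these data decisions could be made knowing the arm

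*Combined protocol and SAP*

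**What the plan says.** The Interventions section states "Neither patients, nor investigators, nor statisticians were masked to treatment assignment". The next sentence gives one safeguard: "Lab staff who performed sampling for PCR, basic blood tests and other routine measurement were unaware of treatment information". Under Enrolment procedure, the randomisation rules were "implemented by an independent statistician who was not involved in data analysis", so the only statistician described as independent took no part in the analysis.

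Four places bear on what was left to decide once data were in hand:

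- **Deviation (Enrolment procedure).** "During follow up 13 patients were found to be deviated from advised therapy", and these patients are outside the final 500. The section does not define deviation, give the split by arm or say who decided.
- **CRP (Operational definitions; Outcomes).** A raised CRP counts as progression in both places, with no cut-off or required change.
- **Window (Outcomes; Operational definitions).** Outcomes limits the primary outcome to five days from the start of treatment. Operational definitions says "appearance of infiltrates on CXR during course of treatment was labeled as progression irrespective of PCR status". Interventions describes the HCQ course as day one plus five further days and gives no length for the standard-of-care course.
- **Test (Statistical analysis).** "We used t-test and chi-square test as appropriate to the nature and distribution of the variables", with the rule "A p-value < 0.05 was considered statistically significant". The Sample size calculation sets the level "at a two-sided significance level of" 0.05. No test is tied to the primary outcome.

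No analysis set, masked derivation or dataset lock is described.

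**The concern.** In an open-label trial the patient and the treating clinician know the arm. Whoever turns the records into an event status and an analysis set need not. Here that protection is given up while some inputs to the primary comparison have no written rule. An analyst who sees the code can, without intending to, settle a borderline CRP value, a late event or a doubtful deviation by its effect on the difference between arms. The single threshold of 0.05 would then no longer carry a 5% false-positive rate.

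The point concerns derivation and analysis. Who judges breathlessness or reads the X-ray is a separate matter.

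**Working it through.** **Figures in the plan.** The flow reconciles: 540 − 20 − 13 − 7 = 500 = 349 + 151. The 13 deviators are 13/540 = 2.4% of those randomised. The HCQ course is 1 + 5 = 6 days against a window of 5. Depending on whether the first treatment day is counted as day 0 or day 1, the two windows may differ by about one day or coincide. The text does not say, and for controls the course has no stated length.

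**Method.** Trials with no treatment effect were simulated, 20,000 per setting, with 349 and 151 patients. For event counts a and b in arms of n1 and n2, N = n1 + n2:

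X² = N·[a(n2 − b) − b(n1 − a)]² / [(a + b)(N − a − b)·n1·n2], with p from chi-square on 1 df.

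The false-positive rate is the share of trials in which the smallest p among the options left open is below 0.05, in either direction.

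**Assumptions (none are in the documents).**

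- Non-CRP progression by day 5 has rate r = 2, 5, 10 or 20%.
- The longer window lets a further 0.25r of patients qualify.
- Three candidate CRP cut-offs flag 0.5r, r or 2r of patients, independently of the other criteria.
- The 13 deviators split 9 HCQ to 4 control and behave like everyone else.
- The locked reference uses the 5-day window and the middle cut-off, with deviators out. Its total event rate is 1 − (1 − r)², which runs from 1 − 0.98² = 4.0% to 1 − 0.80² = 36%.

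**Results (false-positive rate, %).**

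| Left open | r = 2% | 5% | 10% | 20% |
|---|---|---|---|---|
| Nothing (locked) | 4.9 | 5.1 | 5.0 | 5.1 |
| Continuity correction or not | 4.9 | 5.1 | 5.0 | 5.1 |
| Deviators in or out | 5.5 | 5.8 | 5.8 | 5.8 |
| Window | 6.3 | 6.6 | 6.5 | 6.8 |
| CRP cut-off | 9.6 | 10.0 | 10.1 | 10.6 |
| CRP cut-off and window | 12.3 | 12.7 | 13.0 | 13.6 |
| All of these | 13.5 | 14.3 | 14.8 | 15.4 |

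The simulation standard error near 5% is √(0.05 × 0.95/20,000) = 0.15 percentage points. A second simulation of the window alone (10% by day 5 plus an assumed 0.5 to 2 points on day 6) gave 6.3 to 7.1%.

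The test row equals the locked row because the continuity-corrected p is never the smaller of the two. For a yes/no outcome, chi-square is the natural choice of the two named tests. The undefined CRP cut-off carries most of the inflation.

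**The case against.** The strongest reply is that the root cause is missing pre-specification rather than masking. The locked row returns about 5% with no masking imposed, and an unmasked analyst with complete rules has little left to choose. This largely stands, and fixing the rules does much of the work. Masking adds protection for patient-level calls that a written rule does not fully settle.

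Other replies stand in part:

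- Laboratory staff were masked, so measured CRP, ALC and PCR values are protected. The later choice of what counts as raised is not. The exclusion criteria use 6 mg/dl at day 0, but nothing carries that figure into the progression definition.
- The Outcomes section does give a five-day window, and the last scheduled X-ray is on day 5. The window is therefore a small source, as its row shows.
- Deviation from HCQ cannot be classed with HCQ records removed. This is correct, and the fix allows for it.
- The text is in the past tense with final counts. What is missing is any documented rule fixed beforehand; the decisions may already have been made.

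Four stronger readings are tempting, and the documents do not support them:

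- *Outcomes or exclusions were steered.* Arm-dependent scenarios give large rates under no effect at assumed event rates of 5 to 20%. Classifying 2 points fewer events on HCQ (0.02 × 349 ≈ 7 patients) gives 9.0 to 22.3%, and removing 6 HCQ progressors as deviators gives 7.3 to 18.7%. These assume systematic bias, and nothing in the text shows it.
- *A generic best-of-several calculation gives the size.* With latent correlations of 0.8 to 0.95 it yields 8 to 10% for two endpoint versions and 13 to 16% for four. The plan does not set out four such versions. At a 10% rate these correlations mean that two versions share only 56 to 78% of events, less overlap than a one-day extension implies.
- *Masked derivation would restore 5%.* It would not in this trial. Interventions says that patients who refused or had contraindications to HCQ served as controls.
- *Open-label treatment is itself the fault.* It is not.

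**Conclusion.** The concern holds in a limited form. Statisticians were unmasked without need, and deviation status, the CRP criterion and the progression window had no single documented rule, so the nominal 5% is not protected against arm-aware decisions. Taken singly, deviators in or out and the window raise it only to 5.5 to 5.8% and about 6 to 7%. Rates of about 13 to 15% arise only when the CRP cut-off is open too. Choice of test can be set aside.

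These figures rest on the assumed event rates, cut-offs and deviator split, and on the most significant option being picked each time, in either direction. They show size and are not estimates for this trial. This is a worthwhile, inexpensive improvement; it is not evidence that the result is biased.

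**What to change.** 1. State that only patients and treating investigators are unmasked.
2. Reconcile the progression definition and its window across Operational definitions and Outcomes, including what counts as raised CRP. Fix them in writing together with the analysis set and the test for the primary outcome.
3. Derive and sign off progression and PCR status for every randomised patient from listings without treatment code or HCQ records.
4. Have the independent statistician who implemented randomisation merge the code after a dated dataset lock.
5. Keep deviators in the primary analysis as randomised, or class HCQ-specific deviations only after outcomes are signed off.

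If the analysis is already done, the masking sentence should stay as a true record. In that case either re-derive the outcomes as above, or report the unmasked derivation as a limitation with the number of deviators by arm.

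The cost is a treatment-free export, a dated lock and a slightly later analysis, with no added patients or procedures. The change does not remove the bias from non-consenting or contraindicated patients serving as controls. Nor does it address walk tests and X-rays assessed by unmasked staff, for which no masked reading is described.
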